5.0 SELECTION AND WITHDRAWAL OF SUBJECTS

- 5.1 Inclusion Criteria:
 - 5.1.1 ASA I and ASA II children, aged 3-12, with interproximal decay on deciduous molars identified by radiographs. These teeth will not have previous restorations.
 - 5.1.2 Radiographic decay within enamel or extending to the dentin-enamel junction based on International Caries Classification and Management System (ICCMS)¹⁸ Categories 1 through 3 see above. Categories 1, 2 and 3 signify the extent of the "Initial Stages" of an interproximal carious lesion with radiolucency in the outer 1/2 of enamel, inner 1/2 of enamel, and outer 1/3 of dentin respectively.
 - 5.1.3 Interproximal lesions present without existing restorations, recurrent decay, or adjacent teeth with existing restorations.
 - 5.1.4 Behavior of the children should be within a Frankl 3 or 4 category²¹, indicating a "Positive" and "Definitely Positive" behavior rating, which would allow for safe and controlled execution of the proposed protocol.
- 5.2 Exclusion Criteria:
 - 5.2.1 Children who are not ASA I or ASA II.

- 5.2.2 Children who are allergic to or intolerant of SDF
- 5.2.3 Children who have known sensitivity to silver or heavy metal-ions, or have abnormal skin sensitization.
- 5.2.4 Children who have ulcerative gingivitis or stomatitis.
- 5.2.5 Carious interproximal lesions on primary molars in ICCMS Category 4, 5, or 6¹⁸, which signify the extent of the carious lesion radiographically reaching the middle 1/3 of dentin, inner 1/3 of dentin, and into the pulp respectively.
- 5.2.6 Behavior of a child within the Frankl 1 or 2 category²¹, indicating a "Definitely Negative" and "Negative" behavior, which may compromise safe application of SDF.
- 5.3 Withdrawal Criteria
 - 5.3.1 Patients can withdrawal voluntarily at any time.
 - 5.3.2 Any tooth which has progression of caries beyond ICCMS Category 3 will be withdrawn from the study. These teeth will be treated with appropriate restorative dental treatment according to the standard of care.
 - 5.3.3 Any qualifying tooth that subsequently requires a restoration or extraction due to trauma or exfoliates prematurely will be withdrawn from the study.
 - 5.3.4 Any study tooth whose adjacent tooth exfoliates before the end of this study and exposes the interproximal contact will be withdrawn from the study.

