10.0 CRITERIA FOR EVALUATION AND ENDPOINT DEFINITIONS

The primary outcome is arrest of interproximal caries on a primary molar, as measured by lack of change in ICCMS classification indicating caries progression on radiographic examination, (higher score indicates progression). The outcome will be evaluated at three time points: baseline, 6 months and 12 months. As the treatments cannot be made to appear similar to one another, neither the treating dentist or the patient/parent(s) will be blinded to treatment status. However, evaluation of the outcome will made by comparing time lapse (ie. comparing intial xrays vs. at 6 months vs. at 1 year) bitewing radiographs and visualizing if the carious lesion has remineralized, arrested, or progressed

11.0 SPECIAL INSTRUCTIONS:

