13.0 STATISTICAL CONSIDERATIONS

- 13.1 The proposed pilot Phase III randomized controlled clinical trial aims to determine which of the following treatments is superior in arresting dental caries among patients presenting with interproximal caries scoring RA1 RA3 on the International Caries Classification and Management System (ICCMS): (1) Fluoride varnish (FV, current standard of care, control), (2) Super floss + SDF + FV, (3) SDF + FV. We hypothesize that group 2 will have the best outcomes, as measured by no change or reversal in ICCMS classification indicating no caries progression or remineralization on radiographic examination, (higher score indicates progression) followed by group 3. As we could find no data on ICCMS-defined progression or remineralization rates for either Super Floss or fluoride, we were unable to calculate power. Instead, we provide estimates of recruitment based on feasibility. We expect to accrue approximately 20 participants, with 2 qualifying teeth per participant, in each group.
- 10% loss to follow up has increased dramatically to ~48%. Given this unexpected setback, we now need to continue recruiting participants to reach sufficient power. We originally planned to enroll 39 subjects in the study, but would now like to add 21 new participants for a total of 60 participants.

Descriptive statistics will be calculated for all demographic and clinical characteristics to assess the degree to which randomization was successful using means and standard deviations or medians and interquartile ranges for continuous variables and counts and percentages for categorical variables.

The primary analysis will be by intent-to-treat. The primary outcome is the change in ICCMS category, as assessed by radiographic evidence, from baseline to 12 months, with a planned interim analysis to evaluate the endpoint at 6 months for early indications of efficacy. We will calculate the median difference at each time point and use an individual-level model with an adjustment to the standard error to account for the clustering. First we will evaluate the association between treatment groups and the change in ICCMS score from baseline at 6 and 12 months using a cluster-adjusted chi-squared test. We will further assess

14

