the relationship between these two variables using generalized estimating equations, specifying a Poisson (or negative binomial, if overdispersed) family and a log link. We will also specify an exchangeable correlation matrix and a robust standard error.

Since the study is randomized, we do not anticipate needing to adjust for any confounders. However, should we find any differences in demographic or clinical variables at baseline, we will investigate them as potential confounders, which will be defined as those variables which alter the odds ratio by >15% when included in the model.

For those with missing data on outcomes or other covariates to be included in the model, we will consider multiple imputation methods if the amount of missing data is <10%. To assess the impact of missing data, we will compare those with missing data to those not missing data with respect to demographic and clinical variables to assess comparability. Should imputation be utilized, a sensitivity analysis will be conducted excluding those for whom data was imputed to assess the impact of imputation.

Model fit will be evaluated by inspection of residuals and influential points. As we are conducting an interim analysis, we will use a two-sided Bonferroni-corrected p-value of a=.025 for statistical significance. Finally, to assess the degree to which the two raters agree with respect to classifying the outcome of the x-rays, we will calculate and report Kappa. All statistical analyses will be done using Stata 15.0 (College Station, TX).

Power Analysis

We calculated power using a cluster-randomized design. We were unable to locate any previous studies examining the impact of these three treatments (or any two) using the same classification system as our outcome. However, we were able to obtain an estimate of 0.0 to 0.25 for the interclass correlation coefficient (ICC) (Honkala et al., 2011). Assuming the mean ICC, and assuming a clinically significant mean difference of 0.2, a standard deviation of 0.2, a covariance of cluster sizes of 0.65, two caries on average per child, and a two-sided adjusted Type I error rate of 0.025 to account for the three time points at which the data will be analyzed, we will have 80% power with 11-12 participants per group, for a total of 33-36 participants (66-72 caries). Since we anticipate significant loss-to-follow-up over the course

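### The only summary of ICCMS change that section 13.1 names on the category scale is a median difference, which will often be 0 and matches neither the arrest endpoint nor the 0.2 mean difference used for sizing

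*Combined protocol and SAP*

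**What the plan says.** Four statements in the combined protocol and SAP bear on the point.

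- **Endpoint, section 10.0:** "The primary outcome is arrest of interproximal caries on a primary molar, as measured by lack of change in ICCMS classification". This describes a proportion of lesions that do not progress.
- **Outcome, section 13.1:** "The primary outcome is the change in ICCMS category, as assessed by radiographic evidence, from baseline to 12 months". This describes a change score in whole categories.
- **Summary and analysis, section 13.1:** "We will calculate the median difference at each time point". The same sentence adds an individual-level model whose standard error is adjusted for clustering. Treatment groups are then compared on the "change in ICCMS score from baseline at 6 and 12 months using a cluster-adjusted chi-squared test", and after that by GEE with a Poisson or negative binomial family, log link, exchangeable correlation and robust standard error.
- **Sizing, Power Analysis:** "assuming a clinically significant mean difference of 0.2", with a standard deviation of 0.2.

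The text does not say whether the median difference is a within-arm change from baseline or a contrast between arms. It nowhere commits to reporting a between-arm difference in mean change or in the proportion arrested.

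**The concern.** The plan defines success as a proportion, sizes the trial on a mean and summarises the outcome by a median. The median is the weak link. Lesions enter in ICCMS categories 1 to 3 and change in whole steps, and the hoped-for result is a change of 0 or below. When more than half the lesions in an arm stay where they were, the median change is 0 and carries no information about how many of the others progressed. Arms in which 55% and 95% of lesions are unchanged have the same underlying median. A non-zero result is little better: sample medians of whole numbers fall on whole or half units, so a difference between two of them is a multiple of 0.5 and can never be near 0.2.

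What is at stake is the readability of the results. The category-scale figure given for each time point could be 0 in every arm of a trial in which the arms really differ by the amount it was sized to find.

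**Working it through.** **1. The plan's own sample size.** Inputs from the Power Analysis: mean difference 0.2, SD 0.2, two-sided alpha 0.025, 80% power, 2 lesions per child, ICC at the midpoint of 0.0 to 0.25 (0.125), and 0.65 for cluster-size variation, read here as a coefficient of variation.

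- Lesions per arm before clustering: 2 × [0.2 × (2.2414 + 0.8416) / 0.2]² = 19.01.
- Design effect: 1 + [(0.65² + 1) × 2 − 1] × 0.125 = 1.2306.
- Lesions per arm: 19.01 × 1.2306 = 23.39, or 11.7 children. With equal cluster sizes the design effect is 1.125, giving 10.7 children.

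The stated 11 to 12 children per arm is reproduced. The trial is sized on a difference in means.

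**2. Lesions likely to be analysed.** Section 13.1 gives 60 children and about 48% loss: 60 × 0.52 = 31.2, or about 10 children and 20 lesions per arm.

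**3. How often both medians are 0.** Section 13.1 says no progression rates were found, so the rates below are assumptions, each giving a mean difference of 0.2. Lesions either progress one category (probability p) or stay unchanged. For a child with two lesions and within-child correlation ρ = 0.125:

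- P(both progress) = p² + ρp(1 − p)
- P(exactly one) = 2p(1 − p)(1 − ρ)
- P(neither) = the remainder

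At p = 0.3 these are 0.11625, 0.3675 and 0.51625. Summing over 10 independent children gives the distribution of progressing lesions out of 20. The median is exactly 0 if at most 9 progress, since a tie at 10 gives 0.5. At p = 0.3, P(10 or more) = 0.059, so the median is 0 with probability 0.941. At p = 0.1 that probability is 1.000 to three decimals. The product is 0.941. With independent lesions, P(10 or more) would be 0.048, so clustering matters little here.

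Repeating the calculation:

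| Progressing, control v treated | Both medians 0, 10 children per arm | 12 per arm | 20 per arm |
|---|---|---|---|
| 25% v 5% | 98% | 99% | >99% |
| 30% v 10% | 94% | 96% | 99% |
| 40% v 20% | 74% | 77% | 86% |
| 50% v 30% | 39% | 41% | 44% |

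Allowing reversals does not rescue the median. With 20% progressing and 5% reversing v 10% and 15% (means 0.15 and −0.05, difference 0.2), a simulation with 12 children per arm gave both medians 0 in 99.8% of trials.

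**4. Which row is plausible?** The planning SD points towards the upper rows but does not settle it. For one-step changes, an SD of 0.2 within an arm means p(1 − p) = 0.04, so p = 0.042 and about 96% of lesions share one value. That SD cannot hold in both arms of such a trial, however: the smallest pooled SD compatible with a mean difference of 0.2 has one arm at 0 throughout and the other at 20% progressing, which gives √(0.2 × 0.8 / 2) = 0.283.

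**The case against.** The strongest reply is that the plan does not rely on the median to compare treatments. The same sentence goes on to a cluster-adjusted model. The chi-squared test and the GEE follow, and both can respond to a shift while every median is 0. The log-link GEE yields a between-arm ratio with a robust standard error, hence an interval. A chi-squared test on change also implies a table of arm by change from which proportions can be read. All of this stands. A reader might infer that the trial could not detect a benefit or say how large it is; the documents do not support that. Whether a Poisson family suits change scores that can be negative is a separate question.

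Next, the median's role is not stated. If it is only a within-arm description, a median of 0 is a true statement and not a failed effect estimate. That also stands, although a description that is 0 in every arm tells the reader little under either meaning.

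Third, a reader might infer that the medians will be 0 in every arm. The documents contain no rates that would establish this, and at 50% v 30% progressing both medians are 0 in well under half of trials.

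Last, ICCMS categories are ordered zones of depth, for which a median is conventional, while a mean assumes equal spacing. This is a fair point against making the mean the lead summary. It does not apply to the proportion without progression.

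What the reply leaves standing is the mismatch. A chi-squared test gives no effect size, and a ratio of means is neither the difference used for sizing nor the difference in arrest that section 10.0 implies.

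**Conclusion.** The point holds as a modest defect in reporting. The one category-scale summary that section 13.1 names is uninformative when most lesions are unchanged, and it corresponds to neither the section 10.0 endpoint nor the planning target. At a true mean difference of 0.2 with about 20 lesions per arm, both medians would be 0 in roughly 94% to 98% of trials if 25% to 30% of control lesions progress, falling to 74% at 40% and 39% at 50%. These figures rest on assumed progression rates, one-step changes, two lesions per child, an ICC of 0.125 and about 10 children per arm remaining after losses. The validity of the planned tests and the sample size are unaffected by this point.

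**What to change.** In section 13.1, in place of or alongside the median difference, specify for each arm at 6 and 12 months:

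- as lead summary, the proportion of lesions without progression in ICCMS category, and the between-arm differences in that proportion with cluster-adjusted confidence intervals;
- as companion to the planning target, the mean ICCMS change and its between-arm differences, also with cluster-adjusted intervals.

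If the median is kept, say whether it is within-arm or between-arm. Since section 5.3.2 provides that "Any tooth which has progression of caries beyond ICCMS Category 3 will be withdrawn from the study", the definition of the proportion should also say how those teeth are counted.

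The cost is wording only: the data are already collected, and no change in sample size follows. The small downside is that mean change treats ordered categories as equally spaced, which is why the proportion should lead.

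### Two tests of the primary outcome share a 0.025 level that corrects only for the two looks, and neither is named as decisive, so the familywise error can exceed 5% if either may support a claim

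*Combined protocol and SAP*

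**What the plan says.** All of this is in Section 13.0 (item 13.1) of the combined protocol and SAP.

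- Outcome: "The primary outcome is the change in ICCMS category, as assessed by radiographic evidence, from baseline to 12 months".
- Looks: besides the final analysis, an earlier efficacy look is built in, "with a planned interim analysis to evaluate the endpoint at 6 months for early indications of efficacy".
- General approach: the plan will "use an individual-level model with an adjustment to the standard error to account for the clustering". The model is not named at that point.
- Method 1, a cluster-adjusted chi-squared test: "First we will evaluate the association between treatment groups and the change in ICCMS score from baseline at 6 and 12 months".
- Method 2: a further assessment of "the relationship between these two variables using generalized estimating equations, specifying a Poisson (or negative binomial, if overdispersed) family and a log link", with an exchangeable correlation matrix and robust standard errors.
- Level: "we will use a two-sided Bonferroni-corrected p-value of a=.025 for statistical significance". The only reason given in the analysis text is the interim analysis.

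No sentence calls either method primary, confirmatory, supportive or a sensitivity analysis, and none says what happens if they disagree.

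**The concern.** Both methods address the same null hypothesis of no difference between arms in the change in ICCMS category, but they measure different things. The chi-squared test responds to any difference in the distribution of change categories; the GEE compares mean level on a log scale. They can therefore give different answers on the same data.

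Two things are at stake. If a significant result on either method is enough for a superiority claim, the plan has four tests at 0.025, not two, and the 5% total is not assured. Whatever the error rate, a plan without a decisive test also allows the verdict to be settled after both p-values are known. The endpoint wording adds to this: Section 10.0 says "The primary outcome is arrest of interproximal caries on a primary molar", while Section 13.1 uses change in category, so the choice of test can shade into a choice of endpoint.

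**Working it through.** **Inputs from Section 13.0.** Two efficacy looks (6 and 12 months); level 0.025 two-sided; difference 0.2; SD 0.2; ICC 0.125 (midpoint of 0.0 to 0.25); 2 lesions per child; cluster-size variation 0.65, read as a coefficient of variation; 80% power; 11-12 children per group.

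**The plan's own figures.**
- Level: 0.05 / 2 = 0.025. The Power Analysis paragraph attributes the same 0.025 to three time points, but one of those is baseline, where there is no change to test. Two looks is the reading that gives 0.025.
- Lesions per arm before clustering: 2 × [(2.241 + 0.842) × 0.2 / 0.2]² = 19.01.
- Design effect: 1 + [(0.65² + 1) × 2 − 1] × 0.125 = 1.2306.
- Children per arm: 19.01 × 1.2306 / 2 = 11.70, so 12. This matches the plan.

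**How far 0.025 stretches.**
- One method, two looks: at most 2 × 0.025 = 0.05; if the looks were independent, 1 − 0.975² = 0.0494.
- Two methods, two looks, either may win: at most 4 × 0.025 = 0.10; if all were independent, 1 − 0.975⁴ = 0.0963. The methods share data, so the true figure is lower.

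**Allowing for correlation.** Normal model, each test exactly at 0.025, success if any of the four is significant. The correlations are assumptions.

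| Between-time correlation | Between-method 0.8 | 0.9 | 0.95 | Methods identical |
|---|---|---|---|---|
| 0.5 | 0.0739 | 0.0666 | 0.0613 | 0.0465 |
| 0.8 | 0.0635 | 0.0572 | 0.0525 | 0.0403 |

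**Simulated null trials.** Three arms, 10 or 20 children per arm, 2 teeth each, ICC 0.125, between-time correlation 0.5 or 0.8, 12,000 trials per scenario. Assumed category rates, not in the documents: for example, reversal / no change / progression of 10/70/20% at 6 months and 15/50/35% at 12 months; in the yes/no version, progression of 25% and 40%. Tests: a Pearson chi-squared divided by an estimated design effect, and a Poisson GEE with robust variance on scores shifted to be non-negative. Each test was calibrated to reject at exactly 0.025, so small-sample error is excluded.

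| Rule | Familywise error |
|---|---|
| One method, both looks | 0.044-0.049 |
| Any of four, 3-4 change categories | 0.071-0.079 |
| Any of four, progression yes/no | 0.055-0.067 |

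Monte Carlo standard error near 0.075 is √(0.075 × 0.925 / 12,000) = 0.0024.

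With uncalibrated p-values the any-of-four figure ran from 0.051 to 0.119. The upper end passes 10% because the robust GEE test is itself liberal in samples this small (0.034-0.062 per look with 3-4 categories). That is a separate problem and is not counted here. Also with uncalibrated p-values, the two methods disagreed at 12 months in about 1-6% of these null trials.

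**If both routes are kept.** Four tests need 0.05 / 4 = 0.0125 each. The plan's formula then gives 2 × (2.498 + 0.842)² = 22.30 lesions per arm, and 22.30 × 1.2306 / 2 = 13.7, so 14 children per group instead of 12.

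**The case against.** The text has more structure than a bare list of two tests. Twelve months is fixed as the primary time point. The analysis paragraph commits to a model with clustered standard errors, and the GEE is the only regression specified. The provisions on confounders, imputation and model fit also attach to a model. A natural reading is a preliminary association test followed by the model that matters. On that reading one test decides and 5% holds. But the opposite reading, in which the chi-squared test leads because it comes first, is also open. An order of steps is not a decision rule.

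A reader might infer that the error rate simply exceeds 5%. The documents do not support that. It follows only if either test may carry a claim, and no sentence says so. With strongly correlated looks and methods, the excess may be a fraction of a point (0.0525 in the table above).

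A reader might also infer that an unblinded team will pick the result. Section 10.0 says only that the treating dentist and the patient or parents are not blinded; the documents do not say whether the analyst is. The point does not need this: seeing both p-values is enough.

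Nor can a firm rate of disagreement under a real effect be given. It would need progression rates by arm, and Section 13.1 reports that none were found.

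Finally, the study is described as a small pilot. That limits the consequences. Even so, Section 13.1 also calls it Phase III, seeks the superior treatment and sets a corrected level, so that level should have a defined meaning.

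**Conclusion.** The concern holds in conditional form. The plan applies two different tests to the same primary outcome at 6 and 12 months, at a level already used up by the two looks, and names neither as decisive. If significance on either supports a superiority claim, the familywise error can exceed 5%: the bound is 10%, and about 5-8% is realistic. If one test alone decides, or both must be significant, the multiplicity bound stays at 5%. In either case, the verdict can be chosen after both results are seen.

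The 5-8% range rests on assumed category rates, assumed between-time and between-method correlations, two teeth per child in the simulation, and tests that hold their nominal level. Each method was treated as a single three-arm test; pairwise arm comparisons are a separate question.

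**What to change.** In Section 13.1:

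1. Name one decisive between-arm test of the 12-month change, preferably the child-clustered regression model, and state which arm contrast it tests. The model must accept negative change scores, because Section 13.1 counts reversal as an outcome and a Poisson model cannot take negative values.
2. State that the superiority conclusion rests on that test alone.
3. Label the cluster-adjusted chi-squared test supportive, with no separate claim.
4. Keep the 6-month interim, using the same named test at 0.025 per look.

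The total is then at most 2 × 0.025 = 0.05, provided the named test holds its level with this few children; a small-sample correction to the robust standard error would help. The level in the power calculation is unchanged, so the stated 11-12 per group stands.

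The cost is a short edit and the loss of the chi-squared test as a second route to significance. Keeping both routes would mean 0.0125 per test and about 14 per group.

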- 1.21 SDF applied with Super Floss can reliably arrest and/or remineralize initial interproximal lesions.
- 1.22 SDF applied with Super Floss will be more effective than SDF applied without Super Floss or fluoride varnish applied alone in arresting initial interproximal caries.

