 - 7.1.2 SDF application with Super Floss *(Intervention Group 2)*: Petroleum jelly will be applied to lips and face to protect the skin from staining. Teeth will then be dried with an air-water syringe or wiped with gauze. Super Floss will be flossed through contact and left in place. The practitioner will apply SDF to the superfloss on the buccal or lingual aspect and then over the occlusal embrasure. Provider can visualize SDF being absorbed to the other end of the superfloss due to the blue tint of the SDF. Super floss will remain between the teeth, allowing the SDF to absorb, for one minute. Super floss is then removed and excess SDF removed with gauze or cotton roll. Fluoride varnish is applied over all teeth afterwards per high risk CRA protocol and current standard of care^{4,5}.
 - 7.1.3 SDF application without Super Floss (*Intervention Control Group 3*): Petroleum jelly will be applied to lips and face to protect the skin from staining. Teeth will then be dried with an air-water syringe or wiped with gauze, and teeth with interproximal caries isolated. SDF will be applied with microbrush over the occlusal embrasure of the interproximal surfaces of the target teeth. Excess SDF removed with gauze or

cotton roll. Fluoride varnish is applied over all teeth afterwards per high risk CRA protocol and current standard of care^{4,5}.

i. This control (secondary aim) is to determine if indirect/nearby SDF application can also be absorbed by the lesion and arrest caries.

7.2 Drug studies:

AGENT	DOSE	ROUTE	DAY	ReRx INTERVAL	NOTES
38% SDF	9.5mg/drop 1 drop = 25 μL	Topical	1	3 months, 6 months, 12 months	
5% Sodium fluoride varnish (2.26% [22,600ppm] fluoride)	22.6mg/mL 1 unit = 0.4mL	Topical	1	3 months, 6 months, 12 months	Fluoride varnish will be applied to each group.

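### Section 13.1 tests only a three-group association and names no Group 2 versus Group 3 contrast, so a significant result would not by itself support the Super Floss claim

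*Combined protocol and SAP*

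**What the plan says.** **Claims.** Hypothesis 1.22 is that "SDF applied with Super Floss will be more effective than SDF applied without Super Floss or fluoride varnish applied alone", and secondary aim 2.2 repeats it. Section 13.1 "aims to determine which of the following treatments is superior in arresting dental caries", lists the arms as "1) Fluoride varnish (FV, current standard of care, control), (2) Super floss + SDF + FV, (3) SDF + FV", and adds "We hypothesize that group 2 will have the best outcomes", with Group 3 next. Section 7.1.3(i) gives Group 3 a purpose of its own: "to determine if indirect/nearby SDF application can also be absorbed by the lesion and arrest caries". Since every arm receives varnish, that question is naturally Group 3 versus Group 1.

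**Analysis.** Section 13.1 will first "evaluate the association between treatment groups and the change in ICCMS score from baseline" "at 6 and 12 months using a cluster-adjusted chi-squared test". It will then assess "the relationship between these two variables using generalized estimating equations" with a Poisson or negative binomial family, log link, exchangeable correlation and robust standard error. It states no pairwise contrast, reference arm, testing order or adjustment across pairs of arms. The two-sided 0.025 level is justified by the interim analysis and the number of time points, not by the number of arms. The power calculation concerns a single mean difference and does not say between which arms.

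**The concern.** A test of association between a three-level treatment and an outcome has the null that all three arms share one distribution. It can reject because Group 2 is best, because Groups 2 and 3 are equal and both beat varnish, because only Group 3 works, or because Group 2 is worst. Only the first of these agrees with hypothesis 1.22.

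The second pattern matters most. It is the possibility that Group 3 was included to examine: SDF placed nearby may reach the lesion without floss. If so, the named test can be significant while the Super Floss claim is false. The reader is then left with the ranking of the arms, and when Groups 2 and 3 are truly equal, chance alone puts Group 2 ahead about half the time.

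**Working it through.** **Inputs (section 13.1, power analysis).** Difference 0.2; SD 0.2; ICC from 0 to 0.25, mean 0.125; 0.65 for variation in cluster size, read here as a coefficient of variation; two lesions per child; two-sided alpha 0.025; 80% power; 11-12 children per group. With 60 recruited and 48% lost equally across arms, 60 × 0.52 / 3 = 10.4 children per arm remain.

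**Reproducing the plan's figure.**
- Lesions per arm before clustering: 2 × (2.241 + 0.842)² × (0.2/0.2)² = 19.0.
- Design effect: 1 + [(1 + 0.65²) × 2 − 1] × 0.125 = 1.231.
- Children per arm: 19.0 × 1.231 / 2 = 11.7. Without the cluster-size term the design effect is 1.125, giving 10.7.

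These round up to 12 and 11, the stated range. The formula compares two groups.

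**Three-group test when Super Floss adds nothing.** Let Groups 2 and 3 be equal and both differ from varnish by δ. The squared deviations from the overall mean, in units of δ², sum to 4/9 + 1/9 + 1/9 = 2/3. The noncentrality is therefore λ = n_eff × (2/3) × (δ/SD)², where n_eff = 2k/1.231 for k children per arm. The 2-df critical value at 0.025 is 7.38. With three outcome categories the test has 4 df. By symmetry, Group 2 leads Group 3 in half of the significant trials.

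| k | δ | λ | significant, 2 df | significant, 4 df | significant and Group 2 ahead, 2 df |
|---|---|---|---|---|---|
| 10.4 | 0.2 | 11.27 | 79% | 68% | 40% |
| 11 | 0.2 | 11.92 | 82% | 71% | 41% |
| 12 | 0.2 | 13.00 | 85% | 76% | 43% |
| 10.4 | 0.1 | 2.82 | 21% | 15% | 11% |
| 12 | 0.1 | 3.25 | 25% | 18% | 12% |

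At δ = 0.15 the 2-df figures are 50% and 57% at 10.4 and 12 children. The 50% point lies at an SDF effect of about 0.75 SD and 0.70 SD respectively.

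**Check with yes/no progression.** The documents give no progression rates, so these are assumptions (varnish / Group 2 / Group 3). The simulation used 20,000 trials, 10 children per arm, exactly two lesions each, ICC 0.125 and a chi-squared test divided by its design effect. The three-group test rejected in 23% at 30/10/10%, 49% at 40/10/10% and 75% at 50/10/10%. A Group 2 versus Group 3 test rejected in 1.4-1.6%. With all arms at 30% the three-group test rejected in 2.5%, so it holds its level for its own null.

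**Power of a direct Group 2 versus Group 3 contrast, before any gate.** The normal deviate is (δ/SD) × √(n_eff/2) − 2.241.
- δ = 0.2: 2.907 − 2.241 = 0.67, or 75%, at 10.4 children; 3.123 − 2.241 = 0.88, or 81%, at 12.
- δ = 0.1: about 22% and 25%.

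If Groups 2 and 3 are equal, the contrast rejects in 2.5%.

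**The case against.** The strongest reply is that this is a gap in specification, not a wrong test. Section 13.1 also plans an individual-level model and a GEE, and a three-level treatment factor in either can yield arm-specific estimates. The two-group power formula suggests that pairwise comparison was in mind. The comparison with the other arms is the secondary aim, and the protocol calls the study a pilot and preliminary. All of that is fair. Still, being able to produce a contrast is not the same as naming it as the basis of a claim. If varnish, the arm section 13.1 labels control, is the reference, the default coefficients are Group 2 versus 1 and Group 3 versus 1. The Super Floss comparison is the one left out.

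Three stronger readings are tempting, and the documents do not support them.
- *The plan has a rule that turns a significant association with Group 2 ranked first into Super Floss superiority.* No such rule is written. The plan is silent on how a claim would be reached.
- *The 79-85% is a type I error, some thirty times the nominal 2.5%.* In that scenario the three-group null is false, so rejecting it is correct power. The figure relevant to a mistaken Super Floss claim is 40-43%, and it becomes an error only if someone draws that inference.
- *The test will usually be significant whenever SDF works.* That holds near the planned effect of one SD. At 0.1, and at several of the assumed progression rates, the chance is below one half.

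**Conclusion.** The concern holds as a mismatch between hypothesis and test. Whatever the size of the SDF effect, rejecting the three-group null does not show that Group 2 differs from Group 3, and no analysis in section 13.1 is designated to show it. How often this would matter does depend on the effect: significant with Group 2 ahead although floss adds nothing in about 40-43% of trials at the planned 0.2, and 11-12% at 0.1 (2 df, 10.4-12 children per arm). These figures assume ICC 0.125, 0.65 as a coefficient of variation, equal losses across arms and a large-sample approximation on a continuous scale. Whole-number ICCMS categories will behave less smoothly. The same gap leaves the Group 3 question in 7.1.3(i) without a named test.

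**What to change.** In section 13.1, keep the three-group test as a gate. If it is significant, test three 1-df cluster-adjusted contrasts, each at two-sided 0.025 and each reported with a confidence interval:
- Group 2 versus Group 3, for the Super Floss claim;
- Group 2 versus Group 1, for superiority over standard care;
- Group 3 versus Group 1, for the question in 7.1.3(i).

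With three arms this is a closed procedure, so alpha needs no further split across pairs, provided the gate and the contrasts use the same outcome. State that Super Floss superiority over SDF alone is claimed only if Group 2 versus Group 3 is itself significant in favour of Group 2.

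The contrasts need an outcome and model that suit the data. Section 13.1 counts reversal as a good result, so change scores can be negative, and a Poisson log-link model cannot fit them. Progression yes/no is one option, with a method that copes with an arm that has no events. At an assumed 10% progression, two lesions per child and ICC 0.125, a child has no progression with probability 0.9² + 0.125 × 0.09 = 0.821. An arm of ten children then has none with probability 0.821¹⁰ ≈ 0.14, and at least one of two such arms with probability 1 − 0.86² ≈ 0.26.

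The cost is a revision of section 13.1, with no new patients or data. The downside is candour about power: before the gate is applied, Group 2 versus Group 3 has 75-81% power for a difference of 0.2 but only 22-25% for 0.1 at 10.4-12 children per arm. The plan should say so.
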